5.3 Randomization or Treatment Allocation

Single arm phase II study, no randomization

5.4 Stratification

No planned stratification

5.5 Concomitant Medications/Vaccinations (allowed & prohibited)

Medications or vaccinations specifically prohibited in the exclusion criteria are not allowed during the ongoing trial. If there is a clinical indication for one of these or other medications or vaccinations specifically prohibited during the trial, discontinuation from trial therapy or

HCC 18-087

vaccination may be required. The final decision on any supportive therapy or vaccination rests with the investigator and/or the participant's primary physician.

5.5.1 Acceptable Concomitant Medications

All treatments that the investigator considers necessary for a participant's welfare may be administered at the discretion of the investigator in keeping with the community standards of medical care. All concomitant medication will be recorded on the case report form (CRF) including all prescription, over-the-counter (OTC), herbal supplements, and IV medications and fluids. If changes occur during the trial period, documentation of drug dosage, frequency, route, and date may also be included on the CRF.

All concomitant medications received within 28 days before the first dose of trial treatment and 30 days after the last dose of trial treatment should be recorded. Concomitant medications administered after 30 days after the last dose of trial treatment should be recorded for SAEs and ECIs as defined in Section 7.2.

5.5.2 Prohibited Concomitant Medications

Participants are prohibited from receiving the following therapies during the Screening and Treatment Phase of this trial:

- Antineoplastic systemic chemotherapy or biological therapy
- Immunotherapy not specified in this protocol
- Chemotherapy not specified in this protocol
- Investigational agents other than pembrolizumab
- Radiation therapy
 - Note: Radiation therapy to a symptomatic solitary lesion or to the brain may be allowed at the investigator's discretion.
- Live vaccines within 30 days prior to the first dose of study treatment and while participating in the study. Examples of live vaccines include, but are not limited to, the following: measles, mumps, rubella, varicella/zoster, yellow fever, rabies, BCG, and typhoid vaccine. Seasonal influenza vaccines for injection are generally killed virus vaccines and are allowed; however, intranasal influenza vaccines (e.g., FluMist®) are live attenuated vaccines and are not allowed.
- Systemic glucocorticoids for any purpose other than to modulate symptoms from an event of clinical interest of suspected immunologic etiology. The use of physiologic doses of corticosteroids may be approved after consultation with the Sponsor.

Participants who, in the assessment by the investigator, require the use of any of the aforementioned treatments for clinical management should be removed from the study. All treatments that the Investigator considers necessary for a participant's welfare may be

administered at the discretion of the Investigator in keeping with the community standards of medical care.

Medications or vaccinations specifically prohibited in the exclusion criteria are not allowed during the ongoing study. If there is a clinical indication for any medication or vaccination specifically prohibited during the study, discontinuation from study therapy or vaccination may be required. The final decision on any supportive therapy or vaccination rests with the investigator and/or the participant's primary physician. However, the decision to continue the participant on study treatment requires the mutual agreement of the investigator, the Sponsor, and the participant.

There are no prohibited therapies during the Post-Treatment Follow-up Phase.

5.5.3 Rescue Medications & Supportive Care

Participants should receive appropriate supportive care measures as deemed necessary by the treating investigator. Suggested supportive care measures for the management of AEs with potential immunologic etiology are outlined along with the dose modification guidelines in Section 5.2.2, [Table 3]. Where appropriate, these guidelines include the use of oral or IV treatment with corticosteroids, as well as additional anti-inflammatory agents if symptoms do not improve with administration of corticosteroids. Note that several courses of steroid tapering may be necessary as symptoms may worsen when the steroid dose is decreased. For each disorder, attempts should be made to rule out other causes such as metastatic disease or bacterial or viral infection, which might require additional supportive care. The treatment guidelines are intended to be applied when the Investigator determines the events to be related to pembrolizumab.

Note: If after the evaluation of the event, it is determined not to be related to pembrolizumab, the Investigator does not need to follow the treatment guidance. Refer to [Table 3] in Section 5.2.2 for guidelines regarding dose modification and supportive care.

It may be necessary to perform conditional procedures such as bronchoscopy, endoscopy, or skin photography as part of evaluation of the event.

5.6 Participant Withdrawal/Discontinuation Criteria

Participants may discontinue study treatment at any time for any reason or be dropped from the study treatment at the discretion of the investigator should any untoward effect occur. In addition, a participant may be discontinued from study treatment by the investigator or the Sponsor if study treatment is inappropriate, the trial plan is violated, or for administrative and/or other safety reasons. Specific details regarding procedures to be performed at study treatment discontinuation are provided in Section 7.1.4 – Other Procedures

A participant must be discontinued from study treatment but continue to be monitored in the study for any of the following reasons:

- The participant or participant's legally acceptable representative requests to discontinue study treatment
- Confirmed radiographic disease progression outlined in Section 7.1.2.6
- Any progression or recurrence of any malignancy, or any occurrence of another malignancy that requires active treatment
- Significant side effects (such as persistent fever [≥ 101°F (38.3°C) beyond 48 hours after study treatment], catheter infection, or bowel obstruction). Note: Subjects with loss of peritoneal catheter function may choose to have the catheter replaced with up to a 4-week treatment delay
- Unacceptable adverse experiences as described in Section 5.2.2.
- The participant has a medical condition or personal circumstance which, in the opinion of the investigator and/or sponsor, placed the participant at unnecessary risk from continued administration of study treatment.
- The participant has a confirmed positive serum pregnancy test
- Noncompliance with study treatment or procedure requirements
- Recurrent Grade 2 pneumonitis
- Discontinuation of treatment may be considered for participants who have attained a confirmed complete response (CR) and have been treated for at least 6 cycles (at least 22 weeks), receiving at least 2 cycles of the combination including 2 doses of pembrolizumab and at least 80% of the planned doses of IP Cisplatin/IP Rintatolimod beyond the date when the initial CR was declared.
- The participant is lost to follow-up
- Administrative reasons

5.7 Clinical Criteria for Early Trial Termination

Early trial termination will be the result of the criteria specified below:

- 1. Quality or quantity of data recording is inaccurate or incomplete
- 2. Poor adherence to protocol and regulatory requirements
- 3. Incidence or severity of adverse drug reaction in this or other studies indicates a potential health hazard to participants
- 4. Plans to modify or discontinue the development of the study drug

In the event of Merck decision to no longer supply study drug, ample notification will be provided so that appropriate adjustments to participant treatment can be made.

6.0 TRIAL FLOW CHART

6.1 Study Flow Chart

Parameter/ Week	Pre- Treatment ^A	2	5	7	8	11	13	15-16	19	22	Safety Follow-up	31 ^H IP Cath removal	Survival Follow- Up
Cycle		1	2	2	3		4		5	6	4-6 weeks Post Treatment End	End of Study	Every 12 weeks (+/- 4)
Informed Consent	X												1 . , 1 ,
Inclusion/Exclusion Criteria	X												
Baseline Pregnancy Test – see Appendix 3	X												
Baseline TSH, T3/T4	X												
Demographics & Medical History	X												
Prior and Commitment Medication Review	X	X	X		X	X	X		X	X	X		
Full Physical Examination ^B	X						X#						
Directed Physical Examination		X ^I	X		X	X			X	X	X		
Vital signs ^C	X	X	X		X	X	X#		X	X	X		
Height and Weight	X												
ECOG Performance Status	X	X ^I	X		X	X	X#		X	X	X		

Parameter/ Week	Pre- Treatment ^A	2	5	7	8	11	13	15-16	19	22	Safety Follow-up	31 ^H IP Cath removal	Survival Follow- Up
Cycle		1	2	2	3		4		5	6	4-6 weeks Post Treatment End	End of Study	Every 12 weeks (+/- 4)
Adverse Events			X		X	X	X#		X	X	X		.,, .,
CBC with differential, Mag, Phos, LDH, uric acid, CA- 125, and CMP ^{D,}	X	X ^I	X		X	X	X		X	X	X		
Urine analysis	X	X	X		X	X	X		X	X	X		
PT/INR and aPTT	X												
EKG	X	X ^I											
Tumor size CT imaging	X*			X*			X*				X		X*
IP catheter and tumor biopsy	X											X	
Tumor debulking								X					
Cisplatin (IP)		X	X		X	X			X	X			
IP Rintatolimod		X	X		X	X			X	X			
IV Pembrolizumab		X	X		X	X			X	X			
Peritoneal washes ^E	X ^G	X	X		X	X		X	X	X	X	X	

Parameter/ Week	Pre- Treatment ^A	2	5	7	8	11	13	15-16	19	22	Safety Follow-up	31 ^H IP Cath removal	Survival Follow- Up
Cycle		1	2	2	3		4		5	6	4-6 weeks Post Treatment End	End of Study	Every 12 weeks (+/- 4)
Blood (30-40 cc) drawn for in vitro assays ^F	X	X	X		X	X		X	X	X	X	X	
Survival Status **													X

46

A. 28 day screening period to C1D1 unless otherwise noted.

B: Physical examination will be performed by the attending physician or fellow/APP (advanced practice providers).

C: Vital signs (temperature, blood pressure, pulse rate, and respiratory rate) will be taken prior to the administration of each dose of trial treatment.

D: Glucose, BUN, creatinine, sodium, potassium, chloride, CO₂, calcium, total protein, albumin, alkaline phosphatase, AST, ALT, total bilirubin,

E: Peritoneal washes will be collected before IP cisplatin (day 1), before IV pembrolizumab (day 2), before IP rintatolimod (after pembrolizumab, day 2), 1 hour after IP rintatolimod (day 2), the day after IV pembrolizumab/IP rintatolimod (day 3), and day of surgery (peritoneal flushes assist in maintaining peritoneal catheter patency). 2ml sample will be sent for cell count and differential on days 1, 2, 3, at the time of port placement, interval debulking, and port removal if there is greater than 5mL return. Cell count and differential will be collected in a purple top tube.

F: Blood samples (30cc) will be collected within 2 hours (+/- 15min) before IP cisplatin, before IV pembrolizumab, the day after IV pembrolizumab/IP rintatolimod and on day of surgery. For blood collected at procedures (IP port placement, interval surgery, and IP port removal) an additional 10cc will be collected in cell free DNA tubes. Research blood samples are to be collected in a purple top tube.

G: Post-op visit after IP port placement. IP ports are routinely checked for leaking by infusing 500 mL into the port. An attempt to retrieve IP fluid/ ascites will be attempted at each visit.

H: Patients will be considered off study at catheter removal. If catheter is not removed, then patients will be off study following the day 3 catheter wash after the last adjuvant cycle of chemotherapy.

- I: C1D1 labs, and EKG do not need to be repeated if done within 28 days of C1D1. For subsequent cycles, labs/testing should within 2 business days.
- # Activities will occur at this time point, prior to debulking surgery.
- * Imaging will be performed as a part of standard care, after cycle 2 and 4 (week 7 and 13) and 4-6 weeks after completion of therapy, which is a CT imaging of chest/abdomen/pelvis with IV/PO contrast.
- ** Patients will be followed for survival for a period of until death, withdrawal of consent, or the end of the trial, whichever occurs first. This follow up may be done by medical record or phone.

After placement of IP port, ideal start time is days 1-14 after port placement with no more than 21 day window unless wound infection or complications precluding start of treatment. To be approved by PI. Additionally, there is a window of \pm 3 days available for scheduling/rescheduling the remainder of treatments and/or procedures at the discretion of the Subinvestigator, and as discussed with the Investigator if a course is missed or a subject's treatment and/or testing day(s) need to be rescheduled due to the subject's inability to comply with the study calendar (this includes but is not limited to: hospitalizations, business, vacation plans, travel from long distances for study treatment, in advance of the scheduled date to allow ready access to the result(s), reduce financial burden on the subject [i.e. non-UPMC insurance coverage] or reduce travel inconvenience, illness, transportation issues, holidays, family emergencies, etc.).

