3.2 Secondary Objective(s) & Hypothesis(es)

(1) Objective:

Toxicity Endpoints

In addition to clinical and immunologic efficacy, a secondary objective is further monitoring of patient safety and adverse events. Provision is made to suspend the trial if unexpected and serious toxicities occur as outlined in study procedures section. Anticipated toxicities such as renal toxicity or locoregional toxicities of IP therapy will be monitored weekly. Patients will also be closely monitored for immune related toxicities (pneumonitis, colitis, hepatitis, endocrinopathies, nephritis, and infusion related toxicities). Dose adjustments and schedule adjustments will be made according to guidelines for key toxicity parameters, outlined below in study procedures section.

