Pembrolizumab administration

Pembrolizumab 200 mg will be administered as a 30 minute IV infusion on day 2 (Tuesday) of cycles 1-4 of neoadjuvant chemotherapy and adjuvant cycles 5-6.

Sites should make every effort to target infusion timing to be as close to 30 minutes as possible. However, given the variability of infusion pumps from site to site, a window of -5 minutes and +10 minutes is permitted (i.e., infusion time is 30 minutes: -5 min/+10 min).

The Pharmacy Manual contains specific instructions for the preparation of the pembrolizumab infusion fluid and administration of infusion solution.

Rintatolimod administration

Similar to our other phase I protocol (SPORE trial of IPCKM dosage determination, NCT02615574, [name] - Clinical PI; [name]- Translational PI), all patients will receive IP rintatolimod for 4 neoadjuvant cycles (1-4), 200 mg administered over 1-2 hours, and 2 adjuvant cycles (cycles 5-6).

30

Rintatolimod will be administered into an established, semi-permanent access device implanted with a catheter attached to a port in the peritoneal cavity 30 minutes after pembrolizumab. Administered on day 2 (Tuesday) of each cycle by IP infusion at 200mg over 1-2 hours. Each patient will receive infusion for cycles 1-4 of neoadjuvant chemotherapy and adjuvant cycles 5-6.

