AEs associated with pembrolizumab exposure may represent an immunologic etiology. These immune-related AEs (irAEs) may occur shortly after the first dose or several months after the last dose of pembrolizumab treatment and may affect more than on body system simultaneously. Therefore, early recognition and initiation of treatment is critical to reduce complications. Based on existing clinical study data, most irAEs were reversible and could be managed with interruptions of pembrolizumab, administration of corticosteroids and/or other supportive care. For suspected irAEs, ensure adequate evaluation to confirm etiology or exclude other causes. Additional procedures or tests such as bronchoscopy, endoscopy, skin biopsy may be included as part of the evaluation. Based on the severity of irAEs, withhold or permanently discontinue pembrolizumab and administer corticosteroids. Dose modification and toxicity management guidelines for irAEs associated with pembrolizumab are provided in Table 3.

Table 3 Dose modification and toxicity management guidelines for immune-related AEs associated with pembrolizumab

General instructions:

- 1. Severe and life-threatening irAEs should be treated with IV corticosteroids followed by oral steroids. Other immunosuppressive treatment should begin if the irAEs are not controlled by corticosteroids.
- 2. Study intervention must be permanently discontinued if the irAE does not resolve or the corticosteroid dose is not ≤10 mg/day within 12 weeks of the last study intervention treatment.
- 3. The corticosteroid taper should begin when the irAE is \leq Grade 1 and continue at least 4 weeks.
- 4. If study intervention has been withheld, study intervention may resume after the irAE decreased to ≤ Grade 1 after corticosteroid taper.

irAEs	Toxicity Grade (CTCAE v5.0)	Action With Pembrolizumab	Corticosteroid and/or Other Therapies	Monitoring and Follow-up
	Grade 2	Withhold	• Administer corticosteroids (initial dose of 1 to 2 mg/kg prednisone or equivalent)	Monitor participants for signs and symptoms of pneumonitis
Pneumonitis	Recurrent Grade 2, Grade 3 or 4	Permanently discontinue	 followed by taper Add prophylactic antibiotics for opportunistic infections 	Evaluate participants with suspected pneumonitis with radiographic imaging and initiate corticosteroid treatment

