Diarrhea/Colitis	Grade 2 or 3	Withhold	Administer corticosteroids (initial dose of 1 to 2 mg/kg prednisone or equivalent) followed by taper	Monitor participants for signs and symptoms of enterocolitis (ie, diarrhea, abdominal pain, blood or mucus in stool with or without fever)

irAEs	Toxicity Grade (CTCAE v5.0)	Action With Pembrolizumab	Corticosteroid and/or Other Therapies	Monitoring and Follow-up
	Recurrent Grade 3 or Grade 4	Permanently discontinue		and of bowel perforation (ie, peritoneal signs and ileus)
				 Participants with ≥Grade 2 diarrhea suspecting colitis should consider GI consultation and performing endoscopy to rule out colitis Participants with diarrhea/colitis should be advised to drink liberal quantities of clear fluids. If sufficient oral fluid intake is not feasible, fluid and electrolytes should be substituted via IV infusion
AST or ALT Elevation or	Grade 2 ª	Withhold	Administer corticosteroids (initial dose of 0.5 to 1 mg/kg prednisone or equivalent) followed by taper	Monitor with liver function tests (consider weekly or more frequently until liver enzyme value returned to baseline or is stable)
Increased Bilirubin	Grade 3 b or 4 c	Permanently discontinue	Administer corticosteroids (initial dose of 1 to 2 mg/kg prednisone or equivalent) followed by taper	
T1DM or Hyperglycemia	New onset T1DM or Grade 3 or 4 hyperglycemia	Withhold ^d	Initiate insulin replacement therapy for participants with T1DM	Monitor participants for hyperglycemia or other signs and symptoms of diabetes

irAEs	Toxicity Grade (CTCAE v5.0)	Action With Pembrolizumab	Corticosteroid and/or Other Therapies	Monitoring and Follow-up
	associated with evidence of β-cell failure		Administer antihyperglycemic in participants with hyperglycemia	
	Grade 2	Withhold	Administer corticosteroids and initiate hormonal replacements as clinically	Monitor for signs and symptoms of hypophysitis (including hypopituitarism and adrenal insufficiency)
Hypophysitis	Grade 3 or 4	Withhold or permanently discontinue d	indicated	
	Grade 2	Continue	Treat with nonselective beta-blockers (eg, propranolol) or thionamides as	Monitor for signs and symptoms of thyroid disorders
Hyperthyroidism	Grade 3 or 4	Withhold or permanently discontinue d	appropriate	
Hypothyroidism	Grade 2, 3 or 4	Continue	Initiate thyroid replacement hormones (eg, levothyroxine or liothyronine) per standard of care	Monitor for signs and symptoms of thyroid disorders

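### Thyroid function is scheduled only before treatment, which does not fit the stated close monitoring of endocrinopathies, so asymptomatic or non-specific thyroid events may be undercounted

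*Combined protocol and SAP*

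**What the plan says.** - **Schedule (Section 6.1).** The only thyroid row is "Baseline TSH, T3/T4", with a single mark in the pre-treatment column. The row for blood count and chemistry is marked repeatedly through treatment. Its footnote gives the panel as "D: Glucose, BUN, creatinine, sodium, potassium, chloride, CO₂, calcium, total protein, albumin, alkaline phosphatase, AST, ALT, total bilirubin", and neither row label nor footnote names a thyroid test.
- **Safety objective (Section 3.2).** "Patients will also be closely monitored for immune related toxicities (pneumonitis, colitis, hepatitis, endocrinopathies, nephritis, and infusion related toxicities". No method or interval is attached.
- **Timing of immune-related events (Section 5.2.2).** These "may occur shortly after the first dose or several months after the last dose of pembrolizumab treatment", and the same paragraph stresses early recognition.
- **Thyroid actions (Section 5.2.2, Table 3).** For hypothyroidism of Grade 2, 3 or 4: "Initiate thyroid replacement hormones (eg, levothyroxine or liothyronine) per standard of care". For hyperthyroidism, with separate lines for Grade 2 and for Grade 3 or 4: "Treat with nonselective beta-blockers (eg, propranolol) or thionamides as" appropriate. The monitoring column for both reads "Monitor for signs and symptoms of thyroid disorders".
- **Laboratory list (Section 7.1.3, Table 6).** T3, T4 and TSH appear under the heading for other tests, without time points. The text below the table gives a 72-hour pre-dose window after cycle 1 and requires results to be reviewed before each dose, but does not say which tests are meant.
- **Exposure (Section 5.2.1).** Pembrolizumab is given "on day 2 (Tuesday) of cycles 1-4 of neoadjuvant chemotherapy and adjuvant cycles 5-6", which is six doses.

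**The concern.** A single pre-treatment thyroid value can show who had abnormal function at entry. It cannot show a change on treatment, because there is no later scheduled value to compare with it. Section 3.2 makes surveillance for endocrine toxicity part of the secondary safety objective, and Section 7.2 counts an abnormal laboratory finding as a possible adverse event. A biochemical abnormality that nobody tests for is therefore an adverse event that is not captured.

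Symptoms are a weak substitute in this population. Section 4.1.2 lists mild fatigue among the side effects of rintatolimod, and patients also receive cisplatin and may have interval surgery. A thyroid event with non-specific symptoms can be put down to any of these.

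Two things are at stake. One is how complete the thyroid adverse event count is in a small trial of a new combination. The other is how early an event that progresses is recognised. There is also a risk of uneven practice: staff who follow the flow chart would not repeat the tests, while staff who read Table 6 with the pre-dose rule might. Patients would then be ascertained differently.

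**Working it through.** The plan states no figure on this point, so there is none to reproduce. The check is a count of flow chart marks, followed by a search for any other text that would schedule a thyroid test.

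**1. Count of scheduled tests (Section 6.1)**
- Thyroid row: pre-treatment = 1 time point.
- Blood count and chemistry row: pre-treatment, weeks 2, 5, 8, 11, 13, 19, 22 and the safety visit = 9 time points.
- Pembrolizumab row: weeks 2, 5, 8, 11, 19, 22 = 6 doses.
- Dosing visits with chemistry marked: 6 of 6. (A footnote lets the cycle 1 day 1 laboratory tests be skipped if done in the previous 28 days.)
- Dosing visits with a thyroid test marked: 0 of 6.

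**2. Length of the gap**
- First to last dose: 22 − 2 = 20 weeks.
- First dose to safety visit, which falls 4 to 6 weeks after the last dose: (22 + 4) − 2 = 24 weeks, to (22 + 6) − 2 = 26 weeks.

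**3. Does any other text close the gap?**
- Table 6 lists the tests but gives no times.
- The 72-hour rule in Section 7.1.3 gives a window but names no tests.
- Section 7.1 treats the flow chart as the summary of what is done at each visit. It allows unscheduled procedures when the investigator finds them clinically necessary. That is permission, not a schedule.
- No other text adds a post-baseline thyroid test.

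**4. Comparison within Table 3**
The liver, kidney and glucose rows each have a marker in the repeated panel: AST, ALT and bilirubin; creatinine; glucose. The two thyroid rows do not.

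**5. Grade of a silent event**
Table 7 (Section 7.2.4) places an asymptomatic event at Grade 1. The Table 3 thyroid rows begin at Grade 2. A purely silent event therefore triggers no Table 3 action. What is lost is its place in the adverse event count and the chance to recognise it before it progresses.

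**6. Illustration only**
The documents give no thyroid event rate. If a proportion p of patients had a silent thyroid event, the expected number is n × p and the chance of at least one is 1 − (1 − p)^n. The values of p are assumptions. The values of n are full enrolment (45) and a stop after the first Simon stage (20).

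| Assumed p | Expected, n = 45 | At least one, n = 45 | Expected, n = 20 | At least one, n = 20 |
|---|---|---|---|---|
| 1% | 0.45 | 36% | 0.2 | 18% |
| 5% | 2.25 | 90% | 1 | 64% |
| 10% | 4.5 | 99% | 2 | 88% |
| 15% | 6.75 | over 99% | 3 | 96% |

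These are events that would occur, not events that would be missed. How many are missed depends on how much discretionary testing is done, which the documents do not fix.

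**The case against.** The strongest reply is that the plan is minimal but coherent. Section 3.2 promises close monitoring without naming a laboratory method. Table 3 supplies a method, signs and symptoms, and uses similar wording for pneumonitis, colitis and hypophysitis. The flow chart supports it: vital signs including pulse, and a directed examination, recur at the dosing visits and the safety visit, and adverse event review runs from week 5. Section 7.1.2.1 allows more frequent assessment when indicated, Section 5.2.2 asks for adequate evaluation of any suspected immune-related event, and Section 7.1 permits unscheduled tests.

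Much of this stands, and it rules out three stronger readings that a reader might infer.

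- **That thyroid events will go wholly unseen.** Symptomatic events can be found clinically, and discretionary tests can find others. The supportable statement is that no scheduled test would detect them.
- **That Table 3 actions are missed for silent events.** By Table 7 such events are Grade 1, below the level at which the thyroid actions start.
- **That the trial's conclusions are threatened, or that a given number of patients would be missed.** The primary endpoint is radiological response and the Simon rule counts responders. The listed dose-limiting toxicities are tied essentially to cycle 1. The SAP specifies no separate endocrine rate, and any count of missed patients would rest wholly on assumed event and recognition rates.

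What the reply does not remove is the mismatch itself. Every safeguard it cites needs a suspicion first, and a silent event gives none. It also leaves open whether the thyroid tests in Table 6 are meant to recur.

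**Conclusion.** The point holds as a gap between the stated safety objective and the schedule, together with an ambiguity about repeat testing. There are no scheduled thyroid values after the first of six doses, over 20 weeks to the last dose and 24 to 26 weeks to the safety visit, against chemistry marked at all six dosing visits. The likely effect is incomplete counting of asymptomatic or non-specific thyroid events under the secondary safety objective, and later recognition of those that progress. Its size in patients cannot be derived from the documents.

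The conclusion rests on reading the flow chart as the governing schedule. If Section 7.1.3 was meant to require thyroid tests before each dose, the defect is one of drafting and only the text needs correcting. The primary endpoint and the Simon design are untouched. The toxicity suspension rule is touched only to the extent that a cycle 1 thyroid event might qualify as an autoimmune reaction of Grade 2 or more. This should be corrected, but it is not a reason to doubt the efficacy analysis.

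**What to change.** Reconcile Section 3.2, Table 3, the flow chart in Section 6.1, and Table 6 with its pre-dose rule in Section 7.1.3, so that all four say the same thing about thyroid testing after baseline. Two routes would do this.

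- **Schedule it.** The sponsor enters post-baseline thyroid testing in the flow chart at times it chooses, drops the baseline-only label from the row, and states in Section 7.1.3 which tests the pre-dose rule covers. Blood already drawn for chemistry can be used, so no new visit or procedure is needed. The cost is an amendment, a small assay cost, and some additional Grade 1 laboratory events on record.
- **Narrow the claim.** If later testing is not intended, amend Section 3.2 so that it does not imply laboratory surveillance of thyroid function, mark the Table 6 thyroid tests as baseline only, and report thyroid events as symptom-detected. This costs only text, but the safety report must then say that silent events were not sought.

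Which route to take, and any testing interval, is for the sponsor to decide.
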